9.3.5 Multiplicity adjustment (if applicable)

Not applicable.

9.3.6 Sensitivity analyses

Not applicable.

9.3.7 Supplementary analysis

If the primary endpoints of subject-level sensitivity and specificity are met, following supplementary analyses will be conducted.

- TP, FP, FN, TN, sensitivity, specificity and corresponded exact 95% CI will be shown for each 3 central readers respectively.
- If there are participants with not evaluable [⁶⁸Ga]Ga-DOTA-TATE PET/CT imaging, those participants' results will be assumed all positive or all negative respectively and each analysis will be performed for primary endpoints.
- The subgroup analyses using descriptive statistics and 95% CI to assess the homogeneity of the diagnostic performance of [⁶⁸Ga]Ga-DOTA-TATE PET/CT imaging across demographic and baseline disease characteristics will also be performed. Important subgroups will be specified in the SAP.

9.4 Secondary endpoint(s)/estimand(s) analysis

The secondary objectives of the study are described in [Table 3-1](#).

Efficacy analyses will be performed for the EFF.

9.4.1 Efficacy and/or pharmacodynamic endpoint(s)

Subject-level assessments

Subject-level positive predictive values (PPV) is defined as the proportion of TP participants among [⁶⁸Ga]Ga-DOTA-TATE PET/CT imaging positive participants (i.e. TP or FP participants).

Subject-level negative predictive values (NPV) is defined as the proportion of TN participants among [⁶⁸Ga]Ga-DOTA-TATE PET/CT imaging negative participants (i.e. TN or FN participants).

Subject-level accuracy is defined as the proportion of TP and TN participants among all patients in the EFF (i.e. TP+TN+FP+FN participants).

Subject-level PPV, NPV, accuracy will be summarized respectively with corresponded exact 95% CI.

Region-level assessments

Region-level sensitivity is defined as the proportion of [⁶⁸Ga]Ga-DOTA-TATE PET/CT imaging positive regions (TP regions) among CIM positive regions (i.e. TP or FN regions).

Region-level specificity is defined as the proportion of [⁶⁸Ga]Ga-DOTA-TATE PET/CT imaging negative regions (TN regions) among CIM negative regions (i.e. TN or FP regions).

Region-level PPV is defined as the proportion of regions which are positive on both [⁶⁸Ga]Ga-DOTA-TATE PET/CT imaging and CIM (TP regions) among [⁶⁸Ga]Ga-DOTA-TATE PET/CT imaging positive regions (i.e. TP or FP regions).

Region-level NPV is defined as the proportion of regions which are negative on both [⁶⁸Ga]Ga-DOTA-TATE PET/CT imaging and CIM (TN regions) among [⁶⁸Ga]Ga-DOTA-TATE PET/CT imaging negative regions (i.e. TN or FN regions).

Region-level accuracy is defined as the proportion of regions which are CIM and [⁶⁸Ga]Ga-DOTA-TATE PET/CT imaging positive (TP regions) or negative (TN regions) among regions detected by CIM and [⁶⁸Ga]Ga-DOTA-TATE PET/CT imaging (i.e. TP+TN+FP+FN regions).

Where TP, FP, TN, FN regions are defined as follows:

- TP regions are the regions which show at least one lesion based on both [⁶⁸Ga]Ga-DOTA-TATE PET/CT imaging and CIM by central read.
- FP regions are the regions which show at least one lesion based on [⁶⁸Ga]Ga-DOTA-TATE PET/CT imaging but do not show any lesion based on CIM by central read.
- TN regions are the regions which do not show any lesion based on both [⁶⁸Ga]Ga-DOTA-TATE PET/CT imaging and CIM by central read.

- FN regions are the regions which do not show any lesion based on [⁶⁸Ga]Ga-DOTA-TATE PET/CT imaging but show at least one lesion based on CIM by central read.

Region-level sensitivity, specificity, PPV, NPV, accuracy will be summarized respectively with corresponded exact 95% CI by regions. Region consists of liver, pancreas, gastrointestinal, lymph nodes and others.

Number of lesions detected by imaging

For region-level, number of lesion detected by [⁶⁸Ga]Ga-DOTA-TATE PET/CT imaging and CIM will be counted. Regarding [⁶⁸Ga]Ga-DOTA-TATE PET/CT imaging, individual and mean number of lesions detected by each 3 central readers will be presented. Regarding CIM, each number of lesions detected by [¹¹¹In]In-Pentetreotide SPECT/CT and High Resolution CT with contrast (or MRI if CT with contrast is medically contraindicated) will be presented.

Impact on treatment decision

Numbers and percentages of participants for each intended treatment plan collected from physician at pre and post [⁶⁸Ga]Ga-DOTA-TATE PET/CT imaging will be summarized. Summary statistics of participants for the change of intended treatment plan will also be presented.

Inter-reader variability

Inter-reader variability for [⁶⁸Ga]Ga-DOTA-TATE PET/CT imaging is defined as agreement rate among reader determinations and will be assessed by Fleiss' Kappa statistics. Inter-reader variability (%) and its normality 95% CI will be presented.

Lesion-level concordance rate for SSTR

The lesion-level concordance rate for SSTR between [⁶⁸Ga]Ga-DOTA-TATE PET/CT imaging local read and local histopathology result among lesions which is available, will be calculated. The rate is defined as the proportion of lesions which are positive or negative on both local read of [⁶⁸Ga]Ga-DOTA-TATE PET/CT imaging and local histopathology among lesions detected by local histopathology.

9.4.2 Safety endpoints

For all safety analyses, the safety set will be used. All listings and tables will be presented by group (i.e. Patients with confirmed/suspected NENs and HVs).

Safety summaries (tables, figures) include only data from the on-treatment period with the exception of baseline data which will also be summarized where appropriate (e.g. change from baseline summaries). In addition, a separate summary for death including on treatment and post treatment deaths will be provided. In particular, summary tables for adverse events (AEs) will summarize only on-treatment events, with a start date during the on-treatment period (treatment-emergent AEs).

The overall observation period will be divided into three mutually exclusive segments:

1. Pre-treatment period: from day of participant's informed consent to the day before dosing of investigational drug.
2. On-treatment period: from day of dosing of investigational drug to 8 days after dosing of investigational drug.
3. Post-treatment period: starting 9 days after dosing of investigational drug.

Adverse events

The incidence of treatment-emergent adverse events (new or worsening from baseline) will be summarized by system organ class and or preferred term, severity (based on CTCAE grades), type of adverse event, relation to study treatment.

Serious adverse events, non-serious adverse events and adverse events of special interest (AESI) during the on-treatment period will be tabulated.

All deaths (on-treatment and post-treatment) will be summarized.

All AEs, deaths, and serious adverse events (including those from the pre and post-treatment periods) will be listed and those collected during the pre-treatment and post-treatment period will be flagged.

Vital signs

Notable vital sign values will be summarized by visit/time.

12-lead ECG

ECG abnormalities will be summarized.

Clinical laboratory evaluations

Grading of laboratory values will be assigned programmatically as per NCI Common Terminology Criteria for Adverse Events (CTCAE) version 5.0. The calculation of CTCAE grades will be based on the observed laboratory values only, clinical assessments will not be taken into account.

CTCAE Grade 0 will be assigned for all non-missing values not graded as 1 or higher. Grade 5 will not be used.

For laboratory tests where grades are not defined by CTCAE version 5.0, results will be categorized as low/normal/high based on laboratory normal ranges.

The following summaries will be generated separately for hematology, and biochemistry tests:

For laboratory tests where grades are defined by CTCAE version 5.0:

- Worst post-baseline CTCAE grade (regardless of the baseline status). Each participant will be counted only once for the worst grade observed post-baseline.
- Shift tables using CTCAE version 5.0 grades to compare baseline to the worst on-treatment value.

For laboratory tests where grades are not defined by CTCAE version 5.0:

- Shift tables using the low/normal/high/ (low and high) classification to compare baseline to the worst on-treatment value.

Listing of laboratory data will be produced with values flagged to show the corresponding CTCAE version 5.0 grades if applicable and the classifications relative to the laboratory normal ranges.

9.4.3 Pharmacokinetics

Descriptive summary statistics of $[^{68}\text{Ga}]\text{Ga}\text{-DOTA-TATE}$ blood concentration data will be provided by participant, and visit/sampling time point, including the frequency of concentrations below the LLOQ and reported as zero.

Summary statistics will include mean (arithmetic and geometric), SD, CV (arithmetic and geometric), median, minimum, and maximum.

Drug concentrations below LLOQ will be treated as missing for the calculation of the geometric means and geometric CV%, and as zero for all other calculations including calculation of PK parameters.

Descriptive summary statistics will include mean (arithmetic and geometric), SD, and CV (arithmetic and geometric), median, minimum, and maximum.

The PAS will be used in all pharmacokinetic data analysis and PK summary statistics.

Pharmacokinetic variables:

The following pharmacokinetic parameters will be determined using the actual recorded sampling time s and non-compartmental method(s) with Phoenix WinNonlin (Version 6.4 or higher):

AUCinf, AUClast, Cmax, Tmax, T1/2, Lambda_z, CL and Vz.

In addition, the following pharmacokinetic parameters may be determined, if deemed appropriate, using the actual recorded sampling time s and two-compartmental method(s) with Phoenix WinNonlin (Version 6.4 or higher):

[figure not shown]
[figure not shown]
V1, K10, K12, K21, AUC, K10 T1/2, Alpha, Beta, Alpha T1/2, Beta T1/2, V2, CL.

[figure not shown]
[figure not shown]
Bio-fluid concentrations will be expressed in mass per volume units and, if deemed necessary, other units (e.g. radioactivity per volume). All concentrations below the limit of quantitation or missing data will be reported as such in the concentration data listings. Concentrations below the limit of quantitation will be treated as zero in summary statistics.

Pharmacokinetic parameters will be provided by participants. Descriptive statistics of all pharmacokinetic parameters will include arithmetic and geometric mean, median, SD, and CV, geometric CV, minimum, and maximum. Zero concentrations will not be included in the geometric mean calculation. Since Tmax is generally evaluated by a nonparametric method, median values and ranges will be given for this parameter.

Table 9-2 Non-compartmental pharmacokinetic parameters

AUClast	The AUC from time zero to the last measurable concentration sampling time (tlast) (mass x time x volume ⁻¹)
AUCinf	The AUC from time zero to infinity (mass x time x volume ⁻¹)
Cmax	The maximum (peak) observed plasma, blood, serum, or other body fluid drug concentration after single dose administration (mass x volume ⁻¹)
Tmax	The time to reach maximum (peak) plasma, blood, serum, or other body fluid drug concentration after single dose administration (time)
Lambda_z	Smallest (slowest) disposition (hybrid) rate constant (time ⁻¹) may also be used for terminal elimination rate constant (time ⁻¹)
T1/2	The elimination half-life associated with the terminal slope (λ_z) of a semi logarithmic concentration-time curve (time). Use qualifier for other half-lives
CL	The total body clearance of drug from the plasma (volume x time ⁻¹)
Vz	The apparent volume of distribution during terminal phase (associated with λ_z) (volume)

9.6 (Other) Safety analyses

Not applicable.

9.7 Other analyses

Not applicable.

9.8 Interim analysis

Not applicable.

9.9 Sample size determination

9.9.1 Primary endpoint(s)

The primary endpoints of the study are subject-level sensitivity and specificity based on central read.

The sample size was calculated based on the following assumptions for primary endpoints.

- Assumptions for subject-level sensitivity: expected sensitivity of 90% and threshold of 70%
- Assumptions for subject-level specificity: expected specificity of 90% and threshold of 60%

The expected sensitivity and specificity are respectively set as 90% based on the systematic review publication on $[^{68}\text{Ga}]\text{Ga-DOTA-TATE}$ ([Deppen et al 2016a](#)). The thresholds of 70% for sensitivity and 60% for specificity are set by referring to phase III study of $[^{64}\text{Cu}]\text{Cu-DOTA-TATE}$ ([Delpassand et al 2020](#)) and the thresholds will be considered reasonable to show clinical relevant diagnostic performance in this study. For sensitivity, 47 participants with positive result in CIM are required to reject the null hypothesis of sensitivity $\leq 70\%$ with 1-sided alpha level of 2.5% and $\geq 90\%$ power with exact binomial test. For specificity, 23 participants with negative result in CIM are required to reject the null hypothesis of specificity $\leq 60\%$ with 1-sided alpha level of 2.5% and $\geq 90\%$ power with exact binomial test. Therefore, 47

confirmed/suspected NEN patients (expected to be positive in CIM) and 23 HVs (negative in CIM) are required. As a result, 70 participants are required as Efficacy Analysis Set (EFF) in total. The study enrollment will continue until 70 participants in the EFF.

Table 9-3 Sensitivity of power to changes in number of participants

N_Sensitivity	Power for Sensitivity	N_Specificity	Power for Specificity
42	87.9%	28	94.5%
43	86.7%	27	95.3%
44	85.4%	26	96.0%
45	92.4%	25	90.2%
46	91.6%	24	91.5%
47	90.7%	23	92.7%

The N for sensitivity is based on NEN patients with positive result in CIM. The N for specificity is based on NEN patients with negative result in CIM in addition to HVs (i.e., some NEN patients out of 47 patients will be used for specificity estimation instead of sensitivity if the result in CIM is negative).

10 Supporting documentation and operational considerations

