[⁶⁸Ga]Ga-DOTA-TATE will be administered intravenously at a dose of 2 MBq/kg (0.054 mCi/kg) of body weight up to a maximum total dose of 200 MBq (5.4 mCi), and PET/CT imaging will be acquired 40 to 90 minutes after the intravenous injection of [⁶⁸Ga]Ga-DOTA-TATE.

Number of Participants

Approximately 70 participants (47 patients with NENs and 23 HVs) will be enrolled. Of all the participants with NENs, the number of participants with suspected NENs is limited to up to 5 patients with negative CIM by central read.

Key Inclusion criteria

1. Signed informed consent must be obtained prior to participation in the study
2. Participants must be adults \geq 18 years of age
3. ECOG performance status 0-2
4. For patient with NENs only: Participants with confirmed NENs based on histopathology, imaging and other relevant examination, or with suspected NENs which localization cannot be confirmed by CIM
5. For HVs only: Male or female participant in good health condition as determined by no clinically significant findings from medical history, physical examination, vital signs, lab test and ECG

Key Exclusion criteria

1. Inability to complete the needed investigational and conventional imaging due to any reason (severe claustrophobia, inability to lie still for the entire imaging time, etc.)
2. Any additional medical condition, serious intercurrent illness, concomitant cancer or other extenuating circumstance that, in the opinion of the Investigator, would indicate a significant risk to safety or impair study participation
3. Known allergy, hypersensitivity, or intolerance to [⁶⁸Ga]Ga-DOTA-TATE and [¹¹¹In]In-Pentetreotide

4. Therapeutic use of any somatostatin analogue except for the following washout period
 - Short-acting analogs of somatostatin can be used up to 24 hours before injection of [⁶⁸Ga]Ga-DOTA-TATE.
 - Long-acting analogs of somatostatin can be used up to 28 days before injection of [⁶⁸Ga]Ga-DOTA-TATE.
5. Prior administration of a radiopharmaceutical unless 10 or more half-lives have elapsed before injection of [⁶⁸Ga]Ga-DOTA-TATE
6. Use of other investigational drugs within 30 days before screening

Treatment Groups:

All screening procedures must be completed within 35 days prior to imaging day. Enrollment should occur within the 35-days screening period once all eligibility criteria are met.

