5.3.1 Replacement policy

Participants will not be replaced.

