8.1.1 Eligibility screening

- For HVs: The investigator or his/her delegate will confirm that the participant fulfills all the inclusion/exclusion criteria

For NEN patients: The Investigator or his/her delegate will contact the registration center after confirming that the participant fulfills all the inclusion/exclusion criteria. The registration center will confirm the result of CIM by central read and notify the registration to investigators. The registration center will limit the enrollment of patients with negative CIM up to 5. Details will be provided in the registration manual.

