9.1 Analysis sets

The **Full Analysis Set (FAS)** comprises all enrolled participants.

The **Efficacy Analysis Set (EFF)** comprises all enrolled participants who were administered with $[^{68}\text{Ga}]\text{Ga-DOTA-TATE}$. Patients with confirmed/suspected NENs must have both results of $[^{68}\text{Ga}]\text{Ga-DOTA-TATE}$ PET/CT imaging and CIM. HVs must have result of $[^{68}\text{Ga}]\text{Ga-DOTA-TATE}$ PET/CT imaging. If at least 1 central reader cannot judge results for all CIM or $[^{68}\text{Ga}]\text{Ga-DOTA-TATE}$ PET/CT imaging due to imaging quality, the results are considered as "Not evaluable". Those participants will be excluded from the EFF.

The **Safety Set** comprises all participants who received any dose of $[^{68}\text{Ga}]\text{Ga-DOTA-TATE}$.

The **Pharmacokinetic analysis set (PAS)** includes all participants who provided at least one evaluable PK concentration. A profile considered evaluable if all of the following conditions are satisfied:

- Participant received the study drug
- Participant provided at least one primary PK parameter

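### Does stopping enrolment at 70 in the EFF leave specificity without a minimum number of CIM-negative participants?

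*Protocol*

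**What the plan says.** Protocol 9.9.1, repeated in SAP 3, builds the sample size in steps. Sensitivity needs 47 CIM-positive participants. The specificity requirement is separate: "For specificity, 23 participants with negative result in CIM are required to reject the null hypothesis". The text then asks for 47 NEN patients and 23 HVs, adds them to an EFF of 70, and closes with "The study enrollment will continue until 70 participants in the EFF".

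The note under Table 9-3 explains how the split can move: "some NEN patients out of 47 patients will be used for specificity estimation instead of sensitivity if the result in CIM is negative". Protocol 8.1.1 caps such patients at five through the registration center. For HVs it describes only a check by the site: "For HVs: The investigator or his/her delegate will confirm that the participant fulfills all the inclusion/exclusion criteria".

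The group sizes also appear as enrolment targets, for example in Protocol 1.1: "Approximately 70 participants (47 patients with NENs and 23 HVs) will be enrolled". Two other rules bear on who ends up in the EFF. Under Protocol 9.1, if at least one central reader cannot judge the images, the participant counts as not evaluable: "Those participants will be excluded from the EFF". Protocol 5.3.1 adds: "Participants will not be replaced".

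**The concern.** The two co-primary endpoints have separate denominators, but the stop sentence counts only their sum. Planned HV enrolment (23) equals the number that specificity needs, so one HV with an unreadable scan uses up the whole margin. The stop sentence does not say that the next participant must be an HV. The no-replacement rule could even be read as forbidding it. No HV count at registration is described, and the registration manual is not part of the documents.

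The stake is power on a co-primary endpoint. Going from 23 to 22 CIM-negative participants costs about ten points, and Table 9-3 shows no row below 23 to warn the reader.

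**Working it through.** **Inputs.** Success means that the lower limit of the exact 95% CI exceeds 0.7 for sensitivity and 0.6 for specificity (Protocol 9.3.2). Both true values are assumed to be 0.90 (Protocol 9.9.1). One-sided alpha is 0.025.

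**Formulas.** For n participants with x correct results, the Clopper-Pearson lower limit is the 2.5% quantile of Beta(x, n − x + 1). The critical value r is the smallest x whose limit exceeds the threshold p0. The exact binomial test, P(X ≥ r | n, p0) ≤ 0.025, gives the same r at every n checked. Power = P(X ≥ r | n, 0.90). The endpoints use different participants, so the chance of meeting both is the product.

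**The plan's own figures first, then the splits beyond the table.** Every row totals 70.

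| CIM+ / CIM− | r, sens. | Power, sens. | r, spec. | Power, spec. | Both |
|---|---|---|---|---|---|
| 42 / 28 | 36 | 87.9% | 23 | 94.5% | 83.0% |
| 43 / 27 | 37 | 86.7% | 22 | 95.3% | 82.6% |
| 44 / 26 | 38 | 85.4% | 21 | 96.0% | 82.0% |
| 45 / 25 | 38 | 92.4% | 21 | 90.2% | 83.4% |
| 46 / 24 | 39 | 91.6% | 20 | 91.5% | 83.8% |
| 47 / 23 | 40 | 90.7% | 19 | 92.7% | 84.1% |
| *48 / 22* | 41 | 89.8% | 19 | 82.8% | 74.4% |
| *49 / 21* | 41 | 94.8% | 18 | 84.8% | 80.4% |
| *50 / 20* | 42 | 94.2% | 17 | 86.7% | 81.7% |
| *51 / 19* | 43 | 93.6% | 16 | 88.5% | 82.8% |

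The first six rows are those of Table 9-3, and all 12 printed powers reproduce. The italic rows are not in the plan.

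**Why 22 is costly.** At n = 23, 19 correct suffice (lower limit 0.6122). At n = 22, 18 correct fail narrowly (0.5972), so 19 are again needed (0.6509). The exact error rate falls from 0.0190 to 0.0076, and power falls with it. This is the saw-tooth of an exact test: power climbs again at 21, 20 and 19.

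**When 22 can occur.** Let k be the number of CIM-negative NEN patients in the EFF (0 to 5).

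- With 23 HVs in the EFF, specificity has 23 + k participants and sensitivity 47 − k. That gives 23 to 28 and 47 to 42, which is Table 9-3 row for row. A count of 22 is impossible.
- With 22 HVs and 48 NEN patients in the EFF, specificity has 22 + k. With k = 1 the split is again 47/23. Only k = 0 gives 48/22.
- With 22 HVs and 47 NEN patients the EFF holds 69, so under the stop sentence enrolment is still open.

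The shortfall therefore needs three things together: an HV lost from the EFF, the place filled by a CIM-positive patient, and no CIM-negative NEN patient.

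**The case for a change.** The best case for acting is that a site could follow the stop sentence to the letter and still miss the planned power. The group numbers elsewhere in the protocol are approximate and concern enrolment, not the EFF. HVs are also exposed to exclusion: under SAP 2.2 a scan is not evaluable if one region is unreadable and all others are negative, and a true-negative HV has all other regions negative. The documents give no rate of unreadable scans. If one assumes 1%, 2% or 5% per HV, independently, the chance of losing at least one of 23 is 1 − 0.99^23 = 21%, 1 − 0.98^23 = 37% or 1 − 0.95^23 = 69%.

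Part of this stands. The stop sentence does not repeat the split, and Protocol 5.3.1 is not explicitly squared with enrolling until the EFF is full. But those percentages cover only the first of the three conditions. The second requires the sponsor to fill an HV's place with a patient while the same paragraph says that 23 HVs are needed. The two rules are also compatible: no individual is replaced one for one, and enrolment stays open until the target is reached. The protocol's silence on an HV count does not show that none is kept, since 8.1.1 leaves registration details to a manual.

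**Conclusion.** The concern does not hold as a defect in the sample size. Read as a whole, Protocol 9.9.1 and SAP 3 call for 47 NEN patients and 23 HVs in the EFF. On that reading the specificity count runs from 23 to 28, its power is at least 90.2%, and Table 9-3 is complete and correct.

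The 82.8% figure is right for 22 CIM-negative participants, but it describes a split that the paragraph does not intend. Even there the cost would be power only: the exact criterion keeps the one-sided error at 0.0076, below 0.025, so a positive result would be as trustworthy as planned. The chance of ending at 48/22 cannot be computed from the documents.

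What is left is a sentence that omits numbers given just before it. Writing the split into it again would alter no sample size, analysis or printed figure. This conclusion assumes that whoever closes enrolment reads the stop sentence together with the requirements it sums up, and the match between Table 9-3 and 23 HVs supports that.
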